8.14 Potential Drug-Induced Liver Injury

Wherever possible, timely confirmation of initial liver-related laboratory abnormalities should occur prior to the reporting of a potential drug-induced liver injury (DILI) event. All occurrences of potential DILIs, meeting the defined criteria, must be reported as SAEs (see Section 8.7 for reporting details).

Potential DILI is defined as:

1) Treatment-emergent ALT or AST > 3 times ULN,

AND

2) Total bilirubin > 2 times ULN or clinical jaundice, without initial findings of cholestasis (elevated serum alkaline phosphatase),

AND

3) No other immediately apparent possible causes of elevated liver enzymes and hyperbilirubinemia, including, but not limited to, viral hepatitis, pre-existing chronic or acute liver disease, or the administration of other drug(s) known to be hepatotoxic.

8.15 Emergency Medical Support and Patient Card

Patients enrolled in this clinical trial will be provided with Emergency Medical Support cards during their trial participation, which will be furnished by the Sponsor. The Emergency Medical Support card is based on the need to provide clinical trial patients with a way of identifying

themselves as participating in a clinical trial, and subsequently to give healthcare providers access to the information about this participation that may be needed to determine the course of the patient's medical treatment.

This service is designed to provide information to healthcare providers who are not part of the clinical trial. Clinical trial Investigators, who are already aware of the clinical trial protocol and treatment, have other means of accessing the necessary medical information for the management of emergencies occurring in their patients.

The first point of contact for all emergencies will be the clinical trial Investigator caring for the affected patient. The Investigator agrees to provide his or her emergency contact information on the card for this purpose. If the Investigator is available when an event occurs, he/she will answer any questions. Any subsequent action will follow the standard processes established for the Investigators. In cases where the Investigator is not available, the Sponsor will provide a 24-hour contact number, whereby healthcare providers are given access to a physician designated by the Sponsor who can assist with the medical emergency.

8.16 Clinical Laboratory Tests

Clinical laboratory tests will be conducted according to the Schedule of Events (Section 1.2). Clinical laboratory tests for Screening, prior to Day 1 of each cycle thereafter and for Safety Follow-Up Visits will be performed by the central and local laboratories. For eligibility review, if central laboratory tests are cancelled, lost, considered inadequate for analysis, or cannot be processed, local laboratory results provided by the site may be used to determine eligibility. A list of the clinical laboratory analytes to be tested is provided in Appendix 1. Additional clinical laboratory tests may be ordered at the Investigator's or Sub-Investigator's discretion.

Clinical laboratory test data will be reviewed by the Investigator or Sub-Investigator for clinical significance and to make treatment decisions. Any laboratory result deemed clinically significant (i.e., is associated with signs and symptoms, requires treatment, or requires follow-up) will be recorded as an AE as described in Section 8.1.

8.17 Physical Examinations

Physical examinations should be conducted according to the Schedule of Events (Section 1.2). Full physical examinations should be conducted (evaluate all major organ systems, including the following categories: general, head, eyes, ears, mouth/throat, neck, heart, lungs, abdomen, lymph nodes, joints, extremities, integumentary, neurologic, and psychiatric) at Screening. Targeted physical examinations may be focused, at the discretion of the Investigator, to identify changes from baseline or evaluate changes based on the patient's clinical symptoms.

8.18 Vital Signs and Oxygen Saturation

Vital sign measurements will be recorded according to the Schedule of Events (Section 1.2). Vital signs include pulse rate, systolic and diastolic blood pressure, respiratory rate, and

temperature at all time points, as well as pulse oximetry at Screening only. It is preferred that the same arm be used for all blood pressure readings, if possible. Weight is to be reported at each vital sign visit, height at Screening visit only.

8.19 Electrocardiograms

All patients will have 12-lead electrocardiogram (ECG) done during Screening as specified in the Schedule of Events (Section 1.2). ECG data will be locally assessed. After randomization, ECGs will be performed if clinically indicated.

8.20 Echocardiograms

Standard echocardiogram will be performed at Screening to assess cardiac function and LVEF according to the Schedule of Events (Section 1.2). A MUGA scan can be performed to assess cardiac function and LVEF if a standard echocardiogram cannot be performed. After randomization, patients with clinically significant cardiac toxicity should have this assessment repeated as indicated.

9.0 STATISTICAL PLAN

9.1 General Considerations

In general, continuous data will be summarized by descriptive statistics, including number of patients, mean, standard deviation, median, minimum, and maximum. Categorical data will be summarized by the number and percentage of patients. Unless otherwise specified, data will be summarized by treatment arm.

All efficacy endpoints will be analyzed using the ITT population. All safety endpoints will be summarized using the safety population.

A detailed description of analysis methods will be provided in the statistical analysis plan (SAP). The potential impact of COVID-19 on this trial will be assessed. Any changes to the analyses that are required due to COVID-19 will be detailed in the SAP.

9.2 Determination of Sample Size

Up to 950 Stage III/IV melanoma patients at high risk of recurrence will be randomized into the two arms (bempegaldesleukin plus nivolumab vs. nivolumab) in a 1:1 ratio. Enrollment of 950 patients is estimated to take approximately 22.5 months, assuming an enrollment rate of 50 patients/month, with a 7-month of ramp-up.

The sample size is calculated to power the comparison of RFS between the two treatment arms in the ITT population. Based on the RFS results for nivolumab from Bristol-Meyers Squibb study CheckMate-238, a non-constant RFS hazard was observed. Thus, for sample size calculation, a piecewise exponential distribution was assumed in each treatment arm with a constant hazard ratio of 0.7. Specifically, in the nivolumab arm, four different hazard rates were assumed before 3 months, between 3 and 12 months, between 12 and 24 months, and after 24 months, corresponding to RFS rates of 90%, 70.5%, 62%, and 51.7% at 3, 12, 24, and 48 months, respectively. At a two-sided overall alpha level of 0.05, a total of 400 RFS events are needed to detect a hazard ratio of 0.7 with 94% power. The final analysis will occur if 400 events are observed or a minimum follow-up of 45 months is reached, whichever occurs first. Given an enrollment period of 22.5 months, minimum follow-up of 45 months, and a 5% annual dropout rate, a total sample size of 950 patients (475 per treatment arm) is required to observe the needed 400 RFS events at 68 months from first patient first visit (FPFV) for final analysis. It is projected that an observed hazard ratio of 0.811 or less would result in a statistically significant improvement in the final analysis of RFS.

Two formal interim analyses of RFS are planned for this study (Table 12). The first interim analysis will be performed when approximately 320 events (80% of the targeted RFS events for final analysis) are observed, which is expected to be 42 months from FPFV. The second interim analysis will be performed when approximately 360 events (90% of the targeted RFS events for final analysis) are observed, which is expected to be 54 months from FPFV. The stopping boundaries at interim and final analyses will be derived based on the actual number of observed

events using O'Brien and Fleming alpha spending function in software EAST 6.4.1. If the number of events are exactly as planned, the critical p-value boundaries (two-sided) at each planned analysis for 320 RFS events at 42 months from FPFV, for 360 events at 54 months from FPFV (2 interim analyses), and the final analysis (400 events) at 68 months from FPFV are 0.0244 (interim 1), 0.0295 (interim 2), and 0.0383 (final), respectively. The corresponding critical boundaries on hazard ratios are 0.776 (interim 1), 0.793 (interim 2) and 0.811 (final analysis), respectively.

The secondary endpoint of OS will be tested hierarchically given the significance of RFS.

Table 12: Formal Interim Analyses for RFS

Analyses	No. of Events	Time (Month) from FPFV	Critical P-value (2-sided)	Critical HR
1st interim analysis	320	42	0.0244	0.776
2nd interim analysis	360	54	0.0295	0.793
Final analysis	400	68	0.0383	0.811

FPFV = first patient first visit; HR = hazard ratio; No. = number; RFS = recurrence-free survival.

9.3 Analysis Sets

For the purposes of analysis, the following populations are defined in [Table 13](#).

Table 13: Analysis Populations

Population	Description
ITT Population	All patients who are randomized. Patients are grouped within the ITT population according to the treatment to which they are randomized. This is the primary analysis set for baseline characteristics and efficacy endpoints.
Safety Population	All patients who receive at least 1 dose (or partial dose) of study drug. Patients are grouped according to the treatment they actually received. This is the primary analysis set for all safety analyses and drug administration.
PK Population	All patients in the safety population who have evaluable analyte concentration-time profiles that allow for computation of meaningful PK parameter values.
Immunogenicity Population	All treated patients with baseline and at least 1 post-baseline immunogenicity assessment.
Biomarker Population	All randomized patients who have biomarker data available at baseline. For pharmacodynamic biomarkers, the biomarker population includes all randomized patients who have baseline and at least one post-baseline biomarker data available.
HRQoL Population	All patients in the ITT population who had a baseline and at least 1 post-baseline assessment (defined for each instrument).

HRQoL = health-related quality of life; ITT = intent-to-treat; PK = pharmacokinetic.

9.4 Endpoints

9.4.1 Primary Endpoint

The primary endpoint is RFS by BICR, which will be programmatically determined based on the disease recurrence date provided by BICR and is defined as the time between the date of randomization and the date of first recurrence (local, regional, or distant metastasis by BICR), new primary melanoma (by BICR), or all-cause death, whichever occurs first. (Note: a patient who dies without reported recurrence will be considered to have recurred on the date of death.) For patients who remain alive and whose disease has not recurred, RFS will be censored on the date of last evaluable disease assessment. For those patients who remained alive and had no recorded post-randomization tumor assessment, RFS will be censored on the day of randomization. Censoring rules for the primary analysis of RFS are presented in [Table 14](#).

Table 14: Censoring Scheme for Primary Definition of RFS

Situation	Date of Event or Censoring	Outcome
Recurrence (local, regional, distant, new primary melanoma)	Date of first recurrence	Event
Death without recurrence	Date of death	Event
No baseline disease assessment	Date of randomization	Censored
No on-study disease assessments and no death	Date of randomization	Censored
No recurrence and no death	Date of last evaluable disease assessment	Censored
New anticancer therapy (for melanoma or second non-melanoma primary cancer), including melanoma tumor-directed radiotherapy and melanoma tumor-directed surgery, received without recurrence reported prior to or on the same day of disease assessment	Date of last evaluable disease assessment prior to or on the same date of initiation of subsequent therapy	Censored

9.4.2 Secondary Endpoints

Secondary endpoints are presented in [Table 15](#).

Table 15: Secondary Endpoints

Endpoint	Description
OS	Defined as the time between the date of randomization and the date of death due to any cause. Patients who do not have a date of death will be censored on the last date for which a patient was known to be alive. Evaluated in the ITT population.
DMFS by BICR	Defined as the time between the date of randomization and the date of first distant metastasis by BICR or date of death due to any cause, whichever occurs first. For patients who remain alive and distant metastasis-free, DMFS will be censored on the date of last disease assessment. DMFS will be evaluated in patients who are Stage III at study entry.
DMFS by Investigator	Defined as the time between the date of randomization and the date of first distant metastasis by Investigator or date of death due to any cause, whichever occurs first. For patients who remain alive and distant metastasis-free, DMFS will be censored on the date of last disease assessment. DMFS will be evaluated in patients who are Stage III at study entry.
PFS2	PFS2 is defined as time from randomization to progression per Investigator after the start of next line of therapy or death, whichever occurs first. Patients who were alive and without progression after the next line of therapy can be censored at last known alive date. Evaluated in the ITT population. Details on the PFS2 analysis will be described in the SAP.
Overall Safety and Tolerability	Measured by the incidence of adverse events, serious adverse events, deaths, and laboratory abnormalities in the safety population.

Table 15: Secondary Endpoints (Cont'd)

Endpoint	Description
PROs	Measured by (group-level and individual-level) changes from baseline in scores for the GH/QoL and physical functioning subscales of the EORTC QLQ-C30 questionnaire.
PD-L1 Expression as a Predictive Biomarker for RFS	Measured by the RFS by BICR endpoints based on PD-L1 expression level.
RFS by Investigator	Defined similar to the primary endpoint, but recurrence and new primary melanoma are decided by Investigator.

BICR = blinded independent central review; DMFS = distant metastasis-free survival; EORTC QLQ-C30 = 30-item European Organisation for Research and Treatment of Cancer Core Quality of Life Questionnaire; GH/QoL = global health/quality of life; ITT = intent-to-treat; OS = overall survival; PD-L1 = programmed cell death ligand 1; PFS2 = progression-free survival after next line of treatment; PROs = patient-reported outcomes; RFS = recurrence-free survival; SAP = statistical analysis plan.

[REDACTED]

[REDACTED]

[REDACTED]

[REDACTED]	[REDACTED]
[REDACTED]	[REDACTED]
[REDACTED]	[REDACTED]
[REDACTED]	[REDACTED]
[REDACTED]	[REDACTED]
[REDACTED]	[REDACTED]
[REDACTED]	[REDACTED]
[REDACTED]	[REDACTED]
[REDACTED]	[REDACTED]

[REDACTED]

[REDACTED]

[REDACTED]

[REDACTED]

[REDACTED]

[REDACTED]

[REDACTED]

9.5 Demographics and Baseline Characteristics

Demographic data (age, sex, ethnicity, body weight) and baseline disease characteristics will be tabulated, summarized, and presented in data listings.

9.6 Efficacy Analyses

9.6.1 Primary Analyses

A log-rank test stratified by Stage and PD-L1 status will be used to compare RFS between the two treatment arms in the ITT population at an overall alpha level of 0.05 (two-sided). A stratified Cox proportional hazards model with treatment as the single covariate will be used to estimate the hazard ratio and corresponding 95% CI. The Kaplan-Meier method will be used to further summarize RFS, including Kaplan-Meier curves, medians with corresponding 95% CIs, and RFS rates at 6, 12, 18, 24, and every 12 months thereafter with 95% CIs.

Details and additional sensitivity analyses will be described in the SAP.

9.6.2 Secondary Analyses

Only RFS by BICR and OS are formally tested with an overall type I error controlled at 0.05 level via closed sequential testing procedure. If RFS by BICR is statistically significant at any of the planned analyses, the OS endpoint will be tested at 0.05 alpha level when the follow-up time is at least 5 years for all patients.

The secondary analysis of OS in the ITT population will be conducted using a two-sided log-rank test stratified by randomization stratification factors only if the primary analysis of RFS claims significance. A stratified Cox proportional hazards model with treatment as the single covariate will be used to estimate the hazard ratio and corresponding 95% CI. The Kaplan-Meier method will be used to further summarize OS, including Kaplan-Meier curves, medians with corresponding 95% CIs, and OS rates at 6, 12, 18, 24, and every 12 months thereafter with 95% CIs.

To calculate power for the OS comparison, a piecewise exponential distribution can be assumed in each treatment arm with a constant hazard ratio of 0.75. Specifically, in the nivolumab arm, three different hazard rates are assumed before 3 months, between 3 and 36 months, and after 36 months, corresponding to OS rates of 99%, 75%, and 65% at 3, 36, and 60 months, respectively.

The OS endpoint will be tested at a two-sided alpha level of 0.05 only if RFS by BICR is statistically significant at any of the planned analyses and when all patients have the minimum 5-year follow-up, regardless of the number of OS events observed by then. This OS analysis is projected to occur at 83 months from the first patient randomized (~23 months of accrual and 60 months of follow-up based on current enrollment assumptions). Approximately 330 OS events are expected to be observed by then, which will provide 74% power to detect a hazard

ratio of 0.75. The critical hazard ratio is 0.806 if exactly 330 OS events are observed at the time of analysis. The standard Kaplan-Meier estimate and Cox regression model will be used to analyze the OS endpoint.

Under the current enrollment assumptions, it is expected that 177, 229, and 277 OS events will be observed at the first and second interim and the final RFS analysis at 42 months, 54 months, and 68 months from the first patient randomized, respectively.

Other secondary [REDACTED] endpoints will be analyzed similarly to OS. Details of these secondary analyses will be described in the SAP.

To evaluate PD-L1 expression as a predictive biomarker, a Cox proportional hazards model will be used to test the interaction between PD-L1 expression ($\geq 1\%$ vs $< 1\%$) and treatment arm for the RFS endpoints. Additionally, RFS will be analyzed within each PD-L1 expression subgroup ($\geq 1\%$ vs $< 1\%$) including log-rank tests and hazard ratios with corresponding CIs. The Kaplan-Meier method will be used to further summarize RFS, including Kaplan-Meier curves, medians and 95% CIs, and RFS rates in each subgroup at 6, 12, 18, 24, and every 12 months thereafter with 95% CIs. The analyses will be descriptive.

The analysis of EORTC QLQ-C30 data will be performed in the HRQoL population (defined in Section 9.3). Scores for all EORTC QLQ-C30 items and subscales will be linearly transformed to a 0 to 100 metric where higher values indicate better functioning/well-being or lower symptom burden (see EORTC QLQ-C30 Scoring Manual). The primary domains of interest for the HRQoL analysis are GH/QoL and physical functioning of EORTC QLQ-C30.

Scores and post-baseline mean score changes and percent of subjects' HRQoL response status (e.g., improved, worsened, no change) compared to their baseline for the EORTC QLQ-C30 primary subscales will be summarized (e.g., mean with standard deviation and 95% CI, median, minimum, maximum) by treatment group and assessment time point. The clinically meaningful change for group-level analysis will be defined for each EORTC QLQ-30 domain as recommended by the literature (Musoro, 2018), specifically as 7 for GH/QoL and 5 for physical functioning. For individual-level analysis (i.e., percent of subjects who achieved the HRQoL change), the clinically meaningful change thresholds will be defined as 5 (-5) for improvement (deterioration) for both GH/QoL and physical functioning (Cocks, 2015).

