2.2 Scientific Rationale for Study Design

2.2.1 Standard of Care for Melanoma

Treatment for melanoma involves removal of the primary tumor and surrounding normal tissue and sentinel lymph node biopsy to determine stage. Subsequent more extensive lymph node surgery may be necessary if lymph node metastases are present. However, the value of completion lymph node dissection remains controversial. In the Multicenter Selective Lymphadenectomy Trial (MSLT-II), immediate completion lymph node dissection increased the rate of regional disease control and provided prognostic information but did not increase melanoma-specific survival compared to nodal observation with ultrasonography and was associated with higher morbidity ([Faries, 2017](#)). Based on these results, completion lymph-node dissection is no longer a routine standard of care for patients with resected node-positive disease, and regular ultrasound surveillance of the nodal basin is preferred.

Even with complete resection, surgery alone is not sufficient to achieve cure for patients with advanced melanoma. Adjuvant treatment with systemic therapy after surgical resection has attempted to improve survival for patients with higher risk of recurrence over the last two decades. Adjuvant high-dose interferon alpha has been used for many years, but recent meta-analyses including data from a large number of trials have shown only modest

improvements in RFS and OS (Ives, 2017). Over the last several years, multiple new systemic therapies have shown improvements in RFS in the adjuvant treatment for high risk, resected melanoma. Results from these trials are summarized in Table 5.

Table 5: Immune Checkpoint Inhibitor and Targeted Therapy for Adjuvant Treatment of Melanoma: Pivotal Studies

Trial	Stages Included (AJCC 7 th Ed)	Treatment Arms	Median Follow-up	RFS or DFS	DMFS	OS
Immune Checkpoint Inhibitors						
EORTC 18071 Eggermont, 2016 Eggermont, 2019	IIIA>1mm IIB/C	Ipilimumab (n=475) Placebo (n=476)	5 years 7 years	5-year: 41% vs 30% HR = 0.76 7-year: 39% vs 31% HR = 0.75	5-year: 48% vs 39% HR = 0.76 7-year: 45% vs 37% HR = 0.76	5-year: 65% vs 54% HR = 0.72 7-year: 60% vs 51% HR = 0.73
CheckMate 238 Weber, 2017 Weber, 2019 Ascierto, 2020	IIB/C IV	Nivolumab (n=453) Ipilimumab (n=453)	1.5 years 36 months 4 years	1-year: 71% vs 61% HR = 0.65 3-year: 58% vs 45% HR = 0.68 4-year: 52% vs 41% HR = 0.71	1-year: 25% vs 31% HR = 0.73 3-year: NR HR = 0.78 4-year: NR HR = 0.79	NR NR 4-year: 78% vs 77% HR = 0.87

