5.5.2 Survival Follow-up

The Sponsor may request that survival data be collected on all treated/randomized patients outside of the protocol-defined window ([Section 1.2](#)). At the time of this request, each patient will be contacted to determine their survival status unless the patient has withdrawn consent for all contacts or is lost to follow-up. Survival follow-up and patient participation in the study will continue until death, the patient withdraws consent from all further study assessments including survival follow-up, is lost to follow-up, or study termination by the Sponsor.

- All patients will be contacted for survival every 12 weeks (\pm 14 days) following Safety Follow-up Visit 2 (or 100 [\pm 7] days after last dose of study treatment). Survival Follow-up may be conducted in person or by telephone. Alternative methods to determine survival status may be used (e.g., access to medical records and public record searches) as allowed by local regulations and/or guidelines.

- Information about subsequent cancer therapy will also be collected during these contacts. Additional subsequent cancer therapy details such as regimen, setting of the regimen, line of therapy, start date and end date of each regimen, best response to the regimen, and date of progression after next line of therapy may be collected.
- Safety follow-up: Please refer to Section 8.5 and Section 8.7 for details on requirements for safety follow-up that may apply during Survival Follow-up.

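### Does the unstated dropout rate behind the OS projection make the 330 events and 74% power in Protocol 9.6.2 wrong?

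*Protocol*

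**What the plan says.** Protocol Section 9.6.2 sets out the OS planning figures. Control-arm survival is piecewise exponential, "corresponding to OS rates of 99%, 75%, and 65% at 3, 36, and 60 months, respectively", with a constant hazard ratio of 0.75. The test is at two-sided 0.05, only if RFS by BICR is significant, once every patient has five years of follow-up, "regardless of the number of OS events observed by then". That is projected for month 83. The section then says "Approximately 330 OS events are expected to be observed by then, which will provide 74% power", gives a critical hazard ratio of 0.806 at exactly 330 events, and adds that at months 42, 54 and 68 "it is expected that 177, 229, and 277 OS events will be observed". It refers to the current enrollment assumptions but gives no OS dropout rate.

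The only dropout rate in either document is in the RFS sizing sentence of Protocol Section 9.2, "and a 5% annual dropout rate, a total sample size of 950 patients", which SAP Section 6.2 repeats.

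On OS follow-up, Table 15 says that patients without a death date "will be censored on the last date for which a patient was known to be alive". Section 5.5.2 says "All patients will be contacted for survival every 12 weeks", in person or by telephone, and allows medical-record and public-record searches where local rules permit.

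**The concern.** Two projections for the same 950 patients appear to use different dropout rates, and only one rate is disclosed. A reader who carries the 5% from Section 9.2 into Section 9.6.2 cannot reach 330 OS events: the count falls short by about 12% and power falls by about 5 points.

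OS is the only endpoint besides RFS that is formally tested. Because its timing is fixed by follow-up and not by event count, a shortfall would reduce power rather than delay the analysis. If 5% had been intended for OS, the protocol would be overstating the chance of a positive OS result.

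**Working it through.** **Inputs.** From Protocol 9.2: 950 patients, 1:1, 22.5 months of accrual at 50 a month after a 7-month ramp-up. A linear ramp gives 7 × 25 + 15.5 × 50 = 950. From Protocol 9.6.2: control OS 99%, 75% and 65% at 3, 36 and 60 months, hazard ratio 0.75, analysis at month 83. The control monthly hazards are:

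- 0 to 3 months: −ln(0.99)/3 = 0.00335
- 3 to 36 months: −ln(0.75/0.99)/33 = 0.00841
- after 36 months: −ln(0.65/0.75)/24 = 0.00596

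The OS dropout rate d is not stated, so it is varied. It enters as an independent exponential hazard −ln(1−d)/12 per month. Expected events are the integral of hazard × survival × probability of not having dropped out, taken over the accrual pattern and summed over both arms.

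**Power and critical hazard ratio at 330 events.**

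- Power = Φ(√330/2 × |ln 0.75| − 1.96) = Φ(9.083 × 0.2877 − 1.96) = Φ(0.653) = 74.3%
- Critical hazard ratio = exp(−2 × 1.96/√330) = 0.806

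Both stated figures are correct for 330 events.

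**Calibration on RFS.** With the RFS rates of Section 9.2, hazard ratio 0.7 and 5% annual dropout, the same model gives 321, 361 and 400 events at months 42, 54 and 68, against 320, 360 and 400 stated. With no dropout it gives 335, 380 and 429. So the model matches the protocol's method, and the RFS counts do use 5%.

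**OS events at hazard ratio 0.75.**

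| Accrual | Annual OS loss | Month 42 | Month 54 | Month 68 | Month 83 | Power |
|---|---|---|---|---|---|---|
| Stated in 9.6.2 | not given | 177 | 229 | 277 | 330 | 74% |
| Ramp | 0% | 171.5 | 229.1 | 280.4 | 330.4 | 74.4% |
| Ramp | 1% | 169.4 | 225.3 | 274.6 | 322.0 | 73.3% |
| Ramp | 2% | 167.2 | 221.5 | 268.9 | 313.9 | 72.2% |
| Ramp | 5% | 160.8 | 210.5 | 252.4 | 290.7 | 68.9% |
| Uniform | 1% | 177.4 | 231.2 | 279.9 | 326.9 | 73.9% |
| Uniform | 5% | – | – | – | 294.5 | 69.4% |

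The critical hazard ratio is 0.804 at 322 events, 0.802 at 314 and 0.795 at 291.

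**Which loss rate the protocol's counts imply.** Against the four stated counts, the largest deviation is 3.1% with the ramp and no loss (171.5 against 177), and 1.0% with uniform accrual and 1% loss. With the ramp and 5% it is 11.9% (290.7 against 330). The counts were evidently produced with little or no OS loss.

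**What 5% would mean.** About 200 of the 950 patients (21%) would be lost to survival follow-up before death or month 83. At 1% the figure is about 44, and at 2% about 85.

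**The case for a change.** The strongest case for a change is that a planning figure should be reproducible from stated inputs, and this one is not: the reader has to infer near-zero OS loss beside a disclosed 5% for RFS. Nothing in the protocol justifies the difference in words. That stands as an omission.

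It does not show that 330 is wrong. The two endpoints lose information differently. RFS is censored at the last evaluable disease assessment and at new anticancer therapy. OS is censored only at the last date known alive, and that date can be updated by telephone or record search after scans have stopped. Nothing in the documents says that the 5% was meant for OS.

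The 330 might instead be a count under a hazard ratio of 1 with 5% loss, which gives 324.5. It cannot be excluded, but it fits poorly: it implies about 42 events between months 68 and 83 (324.5 − 282.8), where the protocol implies 53 (330 − 277).

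A separate point is that the assumed control OS looks pessimistic. It implies 0.75 × (0.65/0.75)^0.5 = 69.8% at 48 months, while Table 5 reports "4-year: 78% vs 77% HR = 0.87" for adjuvant nivolumab against ipilimumab. With 78% at 48 months and no loss, the count would be 243 to 268, depending on the assumed curve shape. That is a fair sensitivity question, but the earlier trial enrolled 7th-edition Stage IIIB/C and IV, and this one uses 8th-edition staging and adds IIIA with node metastasis above 1 mm. It is a benchmark and does not make the projection an error.

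The SAP also mentions an OS events re-estimation by the DMC (Section 8.0). Its details are left to a charter that is not among the documents, so no defect can be read from it.

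**Conclusion.** No change is needed. Section 9.6.2 omits a detail that a statistician can recover from its own figures: OS loss was taken as zero or close to it. On that reading, 330 events, 74% power and a critical hazard ratio of 0.806 all reproduce. At 1 to 2% a year the projection becomes about 314 to 327 events and 72 to 74% power, a shift of 0 to 2 points on a number the protocol itself calls approximate. The 5% case (about 291 events, 69% power, critical hazard ratio 0.795) is an upper sensitivity bound, not the protocol's OS assumption.

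Nothing in the design turns on the difference. The sample size comes from RFS, the OS test is fixed by follow-up time, and type I error is unaffected. The critical hazard ratio is quoted conditionally on exactly 330 events. The SAP also records early termination after about 774 patients were enrolled and drops all comparative analyses (Sections 3.0, 5.1 and 6.11), so this OS test will not be run.

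The conclusion rests on exponential dropout independent of death, the linear ramp-up (or uniform accrual as the alternative), and the judgement that loss to survival contact is well below 5% a year. The documents support that judgement through their follow-up procedures but do not quantify it.
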